5. SELECTION OF STUDY POPULATION AND WITHDRAWAL CRITERIA

Specific information regarding warnings, precautions, contraindications, adverse events, and other pertinent information on the GSK investigational product or other study treatment that may impact subject eligibility is provided in the mepolizumab Investigator's Brochure (IB) [[GlaxoSmithKline Document Number CM2003/00010/12, 2016](#)].

Deviations from inclusion and exclusion criteria are not allowed because they can potentially jeopardize the scientific integrity of the study, regulatory acceptability or subject safety. Therefore, adherence to the criteria as specified in the protocol is essential.

5.1. Inclusion Criteria

A subject will be eligible for inclusion in this study only if all of the following criteria apply:

AGE

 Between 18 and 70 years of age inclusive, at the time of signing the informed consent.
TYPE OF SUBJECT AND DIAGNOSIS INCLUDING DISEASE SEVERITY

 AD diagnosed by the Eichenfield revised criteria of Hanifin and Rajka [Eichenfield, 2014] (Appendix 3). Diagnosis of AD ≥ 2 years prior to the Screening visit. An IGA score ≥ 3 at the Screening and Baseline visits (Appendix 4). AD involvement of $\geq 10\%$ BSA at the Screening and Baseline visits (Appendix 5). EASI score ≥ 16 at the Screening and Baseline visits (Appendix 6).

- Absolute blood eosinophil count ≥ 350 cells/ μL at the Screening visit.
- Applied the same non-prescription, non-medicated (without an active ingredient) emollient twice-daily for at least 7 days immediately before the Baseline visit.
- Recent history (≤ 6 months prior to the Screening visit) of inadequate response to a stable regimen of prescription topical medication or for whom prescription topical medications are not tolerated or where there is a concern for potential side effects, such as skin thinning or increased risk of hypothalamic-pituitary-adrenal [HPA] suppression; as well as, inadequate response to optimization of nonpharmacological measures such as moisturizers
- **Note:** Inadequate response to a stable regimen of prescription topical medication (such as medium to high potency topical corticosteroids or topical calcineurin inhibitors) is defined as failure to achieve and maintain remission or low disease activity state (equivalent to an IGA score =0 [clear] to 2 [mild]) despite treatment for the recommended duration as per label or for the maximum duration recommended for the subject treatment, whichever is shorter.

SEX

- Male OR Female

Females:

A female subject is eligible to participate if she is not pregnant (as confirmed by a negative urine human chorionic gonadotrophin (hCG) test), not lactating, and at least one of the following conditions applies:

- a. Non-reproductive potential defined as:
 - Pre-menopausal females with one of the following:
 - Documented tubal ligation
 - Documented hysteroscopic tubal occlusion procedure with follow-up confirmation of bilateral tubal occlusion
 - Hysterectomy
 - Documented Bilateral Oophorectomy
 - Postmenopausal defined as 12 months of spontaneous amenorrhea [in questionable cases a blood sample with simultaneous follicle stimulating hormone (FSH) and estradiol levels consistent with menopause (refer to laboratory reference ranges for confirmatory levels)]. Females on hormone replacement therapy (HRT) and whose menopausal status is in doubt will be required to use one of the highly effective contraception methods if they wish to continue their HRT during the study. Otherwise, they must discontinue HRT to allow confirmation of post-menopausal status prior to study enrollment.
- b. Reproductive potential and agrees to follow one of the options listed in the Modified List of Highly Effective Methods for Avoiding Pregnancy in Females of

Reproductive Potential (FRP) (See [Appendix 7](#)) from 30 days prior to the first dose of study medication and until 16 weeks after the last dose of study medication.

The investigator is responsible for ensuring that subjects understand how to properly use these methods of contraception.

INFORMED CONSENT

- Subject is able to give signed informed consent as described in Section [10.2](#) which includes compliance with the requirements and restrictions listed in the consent form and in this protocol.

5.2. Exclusion Criteria

A subject will not be eligible for inclusion in this study if any of the following criteria apply:

CONCURRENT CONDITIONS/MEDICAL HISTORY (INCLUDES LIVER FUNCTION AND QTc INTERVAL)

1. Other types of eczema.
2. Any other concomitant skin disorder (e.g., generalized erythroderma such as Netherton's Syndrome, or psoriasis), pigmentation, or extensive scarring that in the opinion of the investigator may interfere with the evaluation of AD lesions or compromise subject safety.
3. Immunocompromised (e.g., lymphoma, acquired immunodeficiency syndrome, Wiskott-Aldrich Syndrome) or has a history of malignant disease within 5 years before the Baseline visit.

Note: Subjects with successfully treated basal cell carcinoma (no more than 3 lesions), squamous cell carcinoma of the skin, or cervical carcinoma in situ, with no evidence of recurrence within the 3 years prior to the Baseline visit may participate in the study.
4. A positive history for human immunodeficiency virus (HIV) antibody.
5. Chronic or acute infection requiring treatment with oral or IV antibiotics, antivirals, anti-protozoals, or antifungals within 4 weeks before the Screening visit or anytime between the Screening and Baseline visits. Also See Section [6.10.2](#) and [Table 1](#).
6. Superficial skin infections within 1 week before the Screening visit.
7. Known, pre-existing or suspected parasitic infection within 6 months before the Screening visit.
8. Other known or suspected conditions that could lead to elevated eosinophils, for example, hypereosinophilic syndromes including eosinophilic granulomatosis with polyangiitis (EGPA, also known as Churg-Strauss Syndrome), eosinophilic esophagitis, or severe asthma.

9. A history or ongoing serious illness or medical, physical, or psychiatric condition(s) that, in the investigator's opinion, may interfere with the subject's completion of the study.
10. ALT >2xULN
11. Bilirubin >1.5xULN (isolated bilirubin >1.5xULN is acceptable if bilirubin is fractionated and direct bilirubin <35%).
12. Current or chronic history of liver disease, or known hepatic or biliary abnormalities (with the exception of Gilbert's syndrome or asymptomatic gallstones).
13. QTcF >450 msec or QTcF >480 msec in subjects with Bundle Branch Block.
14. Clinically significant abnormality in the hematological or biochemical screen, as judged by the investigator.

CONCOMITANT MEDICATIONS

15. Previously treated with mepolizumab or participated in a previous mepolizumab clinical study.
16. Prior treatment with any of the medications or treatments listed in [Table 1](#) within the indicated periods before the Screening visit.

RELEVANT HABITS

17. Prolonged exposure to natural (e.g, sunlight) ultraviolet (UV) radiation within 4 weeks prior to the Baseline visit and/or intention to have such exposure during the study, which is thought by the investigator to potentially impact the subject's AD.
18. More than 2 visits per week to a tanning booth or parlor in the 4 weeks prior to the Baseline visit.
19. Onset of a new exercise routine or major change to a previous exercise routine within 2 weeks before randomization, or unwilling to maintain current level of physical activity throughout the length of participation in this study.
20. History of alcohol or other substance abuse within the last 2 years.

CONTRAINDICATIONS

21. Hypersensitivity to mepolizumab or any of its excipients.

DIAGNOSTIC ASSESSMENTS AND OTHER CRITERIA

22. Presence of hepatitis B surface antigen (HBsAg), positive hepatitis C antibody test result at screening or within 3 months prior to first dose of study treatment.
23. Exposure to more than 4 investigational medicinal products within 12 months prior to the Baseline visit.
24. Subject is a member of the investigational team or his/her immediate family.

5.3. Screening/Baseline Failures

Screen failures are defined as subjects who consent to participate in the clinical trial but are never subsequently randomized. In order to ensure transparent reporting of screen failure subjects, meet the Consolidated Standards of Reporting Trials (CONSORT) publishing requirements, and respond to queries from Regulatory authorities, a minimal set of screen failure information is required including Demography, Screen Failure details, Eligibility Criteria, and Serious Adverse Events (See Section 7.4.1.5).

Subjects who are screen failures may be re-screened one time.

5.4. Withdrawal/Stopping Criteria

A subject may withdraw from study treatment at any time at his/her own request, or may be withdrawn at any time at the discretion of the investigator for safety, behavioral or administrative reasons.

5.4.1. Early Withdrawal from Study Treatment

Subjects must **permanently discontinue study treatment** for any of the following reasons:

- Subject presents with worsening AD or any other condition that requires treatment with a prohibited medication.
- Subject experiences an adverse event(s) which is considered to be related to study treatment or study procedures and, in the investigator's judgment, is severe enough in nature to warrant treatment discontinuation.
- Subject experiences a cardiovascular or hematologic AE consistent with specific Common Terminology Criteria for AEs (CTCAE) version 4.02 Grade 2 (moderate) or higher (See SRM).
- The subject's randomized treatment assignment is unblinded by the investigator or treating physician.
- Subject becomes pregnant.
- Sponsor request (after discussion with the investigator), for reasons such as a significant protocol deviations or subject noncompliance.
- Study is terminated by the sponsor.
- Subject meets liver chemistry stopping criteria (See Section 5.4.4).
- Subject meets QTcF stopping criteria (See Section 5.4.5).

Subjects who permanently discontinue study treatment will be followed for 8 weeks after the last dose of study treatment. Every effort will be made by the investigator to encourage the subject to remain in the study to complete the two Post-Treatment visits providing that consent has not been withdrawn for subsequent visits.

If the decision is made to permanently discontinue study treatment less than 4 weeks after the last dose, an Early Withdrawal Visit will be scheduled as soon as is reasonably possible. Post-Treatment Visit 1 will then be scheduled 4 weeks after the last dose of study treatment, and Post-Treatment Visit 2 will be scheduled 8 weeks after the last dose of study treatment.

If the decision is made to permanently discontinue study treatment at a scheduled visit and approximately 4 weeks have elapsed since the last dose of study treatment, the procedures of Post-Treatment Visit 1 will be performed. Post-Treatment Visit 2 will be scheduled 8 weeks following the last dose of study treatment.

The investigator will record the primary reason for permanent discontinuation of study treatment and subsequent study withdrawal in the electronic Case Report Form (eCRF).

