6.3. Blinding

This will be a double-blind (sponsor open) study and the following will apply:

- GSK will utilize a blinded study team which will include a blinded study medical monitor and a blinded Operations and Science Lead. In addition, GSK will designate unblinded team members including an unblinded Medical Monitor and an unblinded Global Study Manager to respond to questions or issues involving study treatment assignment and preparation. The unblinded medical monitor may also review unblinded abnormal lab values for safety monitoring. Unblinded GSK study monitors will review unblinded study treatment documentation while blinded GSK study monitors will review blinded records. Procedures will be in place to ensure blinded GSK team members remain blinded.
- Formal Interim Analysis: A formal interim analysis may be performed to enable future planning and to assess futility. It is expected that GSK's study statistician, programmer, clinical scientist, project physician lead, and/or respective designee(s) will be unblinded to subject-level data for the subjects enrolled at the time the database is locked for the formal interim analysis. These persons will not share subject-level randomization assignments with anyone not involved in conducting the analyses. The protection of the study blind and the dissemination plan for summary level results of the interim analyses will be described in the RAP.
- Administrative Interim Analyses: Unblinded in-stream data summaries will be generated by a GSK study statistician and study programmer. The unblinded summaries will be provided to GSK senior manager(s) for their review of subject efficacy and safety data. The results and randomization assignments will only be shared with members involved in the review and conduct of the analysis.
- Study treatment will be prepared by a designated qualified, unblinded member of the site staff who is independent of the protocol-defined study assessments. Unblinded site staff cannot participate in blinded activities (e.g., may not

transition to study coordinator role or other blinded role) at any point throughout the life of the study. They must not have any contact with the study subjects.

- Once prepared, mepolizumab and placebo (0.9% sodium chloride solution provided by the site) will be identical in appearance.
- Blinded site staff will administer study treatment to the subject.
- Procedures must be in place at the study site to ensure that blinding is maintained.

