- In order to maintain the blind, the results from the following laboratory assessments will be blinded during the study: PK, immunogenicity, IL-5, blood biomarkers, and skin biopsy. Additionally, the following will be blinded from the Baseline visit until the end of the study: total WBC count, absolute eosinophil count, and differential (%). Investigators will ensure that subjects and any physicians managing study subjects during the course of the study are informed of this requirement. Absolute neutrophil, lymphocyte, monocyte, and basophil counts will be provided.
- In the event that a local laboratory analyzes a hematology sample for a study subject after the Baseline visit, procedures must be in place at the site to ensure that the results of the total WBC count, absolute eosinophil count, and differential (%) remain blinded to the blinded site staff.
- The investigator or treating physician may unblind a subject's treatment assignment **only in the case of an emergency** OR in the event of a serious medical condition when knowledge of the study treatment is essential for the appropriate clinical management or welfare of the subject as judged by the investigator.
- Investigators have direct access to the subject's individual study treatment.
- It is preferred (but not required) that the investigator first contacts the Medical Monitor or appropriate GSK study personnel to discuss options **before** unblinding the subject's treatment assignment.
- If GSK personnel are not contacted before the unblinding, the investigator must notify GSK as soon as possible after unblinding, but without revealing the treatment assignment of the unblinded subject, unless that information is important for the safety of subjects currently in the study.
- The date and reason for the unblinding must be fully documented in the CRF.
- A subject must permanently discontinue study treatment if that subject's treatment assignment is unblinded by the investigator or treating physician (Section 5.4). The subject will be encouraged to complete the Post-Treatment visits. The primary reason for study treatment discontinuation (the event or condition which led to the unblinding) will be recorded in the eCRF.
- GSK's Global Clinical Safety and Pharmacovigilance (GCSP) staff may unblind the treatment assignment for any subject with an SAE. If the SAE requires that an

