12.8. Appendix 8 – Liver Safety Required Actions and Follow up Assessments

Liver chemistry stopping criteria and required follow up assessments

Liver Chemistry Stopping Criteria - Liver Stopping Event	
ALT-absolute	ALT \geq 8xULN
ALT Increase	ALT \geq 5xULN but <8xULN persists for \geq 2 weeks ALT \geq 3xULN but <5xULN persists for \geq 4 weeks
Bilirubin^{1, 2}	ALT \geq 3xULN and bilirubin \geq 2xULN (>35% direct bilirubin)
INR²	ALT \geq 3xULN and INR>1.5, if INR measured
Cannot Monitor	ALT \geq 5xULN but <8xULN and cannot be monitored weekly for \geq 2 weeks ALT \geq 3xULN but <5xULN and cannot be monitored weekly for \geq 4 weeks
Symptomatic³	ALT \geq 3xULN associated with symptoms (new or worsening) believed to be related to liver injury or hypersensitivity
Required Actions and Follow up Assessments following ANY Liver Stopping Event	
Actions	Follow Up Assessments

 Immediately discontinue study treatment Report the event to GSK within 24 hours Complete the liver event CRF and complete an SAE data collection tool if the event also meets the criteria for an SAE² Perform liver event follow up assessments Monitor the subject until liver chemistries resolve, stabilize, or return to within baseline (See MONITORING below) Do not restart/rechallenge. Permanently discontinue study treatment and may continue subject in the study for any protocol specified follow up assessments (refer to Section 5.4). 	
 Viral hepatitis serology⁴ Blood sample for pharmacokinetic (PK) analysis, obtained within 4 weeks after last dose⁵ Serum creatine phosphokinase (CPK) and lactate dehydrogenase (LDH). Fractionate bilirubin, if total bilirubin \geq 2xULN Obtain complete blood count with differential to assess eosinophilia. Note: This blood sample will be sent to the central laboratory to maintain the blind while study is ongoing. Results will be provided only if unblinding of a subject's treatment assignment is required. Also note that the mechanism of action of mepolizumab leads to lowering of eosinophils.

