- All events of ALT \geq 3xULN **and** bilirubin \geq 2xULN (>35% direct bilirubin) or ALT \geq 3xULN **and** INR>1.5, if INR measured which may indicate severe liver injury (possible 'Hy's Law'), **must be reported as an SAE (excluding studies of hepatic impairment or cirrhosis)**; INR measurement is not required and the threshold value stated will not apply to subjects receiving anticoagulants
- New or worsening symptoms believed to be related to liver injury (such as fatigue, nausea, vomiting, right upper quadrant pain or tenderness, or jaundice) or believed to be related to hypersensitivity (such as fever, rash or eosinophilia)
- Includes: Hepatitis A IgM antibody; Hepatitis B surface antigen and Hepatitis B Core Antibody (IgM); Hepatitis C RNA; Cytomegalovirus IgM antibody; Epstein-Barr viral capsid antigen IgM antibody (or if unavailable, obtain heterophile antibody or monospot testing); Hepatitis E IgM antibody

5. PK sample may not be required for subjects known to be receiving placebo or non-GSK comparator treatments. Record the date/time of the PK blood sample draw and the date/time of the last dose of study treatment prior to blood sample draw on the CRF. If the date or time of the last dose is unclear, provide the subject's best approximation. If the date/time of the last dose cannot be approximated OR a PK sample cannot be collected in the time period indicated above, do not obtain a PK sample. Instructions for sample handling and shipping are in the SRM.

Liver chemistry increased monitoring criteria with continued therapy

Liver Chemistry Increased Monitoring Criteria – Liver Monitoring Event	
Criteria	Actions

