12.11.1. Definition of Adverse Events

Adverse Event Definition:

- An AE is any untoward medical occurrence in a patient or clinical investigation subject, temporally associated with the use of a medicinal product, whether or not considered related to the medicinal product.
- NOTE: An AE can therefore be any unfavorable and unintended sign (including an abnormal laboratory finding), symptom, or disease (new or exacerbated) temporally associated with the use of a medicinal product.

Events meeting AE definition include:

- Any abnormal laboratory test results (hematology, clinical chemistry, or urinalysis) or other safety assessments (e.g., ECGs, radiological scans, vital signs measurements), including those that worsen from baseline, and felt to be clinically significant in the medical and scientific judgement of the investigator.
- Exacerbation of a chronic or intermittent pre-existing condition including either an increase in frequency and/or intensity of the condition.
- New conditions detected or diagnosed after study treatment administration even though it may have been present prior to the start of the study.
- Signs, symptoms, or the clinical sequelae of a suspected interaction.
- Signs, symptoms, or the clinical sequelae of a suspected overdose of either study treatment or a concomitant medication (overdose per se will not be reported as an AE/SAE unless this is an intentional overdose taken with possible suicidal/self-harming intent. This should be reported regardless of sequelae).
- "Lack of efficacy" or "failure of expected pharmacological action" per se will not be reported as an AE or SAE. However, the signs and symptoms and/or clinical sequelae resulting from lack of efficacy will be reported if they fulfil the definition of an AE or SAE.

Events NOT meeting definition of an AE include:

- Any clinically significant abnormal laboratory findings or other abnormal safety assessments which are associated with the underlying disease, unless judged by the investigator to be more severe than expected for the subject's condition.
- The disease/disorder being studied or expected progression, signs, or symptoms of the disease/disorder being studied, unless more severe than expected for the subject's condition.

- Medical or surgical procedure (e.g., endoscopy, appendectomy): the condition that leads to the procedure is an AE.
- Situations where an untoward medical occurrence did not occur (social and/or convenience admission to a hospital).

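### The eosinophil part of the symptomatic liver stop is hidden from the site that must apply it, and no one else is required to apply it

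*Protocol*

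**What the plan says.** **Liver stop (Protocol Appendix 8).** The Symptomatic criterion is ALT at or above 3xULN with symptoms of liver injury or hypersensitivity. Footnote 3 says these must be new or worsening and describes the second kind as "believed to be related to hypersensitivity (such as fever, rash or eosinophilia". The increased-monitoring table lets a subject with ALT from 3xULN to below 8xULN stay on treatment only if, among other conditions, there are no such symptoms. After any liver stopping event a blood count is sent to the central laboratory. The note on that sample reads "Results will be provided only if unblinding of a subject", and goes on to refer to the treatment assignment.

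**Blinding (Protocol 6.3).** To protect the blind, "the following will be blinded from the Baseline visit until the end of the study: total WBC count, absolute eosinophil count, and differential". Local-laboratory results obtained after Baseline must also be kept from blinded site staff. Part of the white-cell picture stays open: "Absolute neutrophil, lymphocyte, monocyte, and basophil counts will be provided". On sponsor review, the section says: "The unblinded medical monitor may also review unblinded abnormal lab values for safety monitoring".

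**Hematologic stop (Protocol 5.4.1).** Permanent discontinuation is required if "Subject experiences a cardiovascular or hematologic AE consistent with specific Common Terminology Criteria for AEs (CTCAE) version 4.02 Grade 2 (moderate) or higher". The list of specific terms is left to the SRM.

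**The concern.** A mandatory stop works only if someone who can see the qualifying sign is obliged to act on it. For eosinophilia, Appendix 8 assumes that the sign can be judged, while 6.3 removes it from view. The role that could bridge the two has an option and not a duty, and no route is written for telling the site that a criterion is met. Followed as written, a subject with raised ALT whose only hypersensitivity sign is a rise in eosinophils could be classed as free of such signs and dosed at the next visit.

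**Working it through.** The plan gives no figure to reproduce. The check compares the texts, then applies two pieces of arithmetic.

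**1. Can the site apply the eosinophil part of the liver stop?** Every subject enters with at least 350 cells/µL (Protocol 5.1), so new or worsening eosinophilia can be judged only by comparing later counts with earlier ones. The site has the Screening count. From Baseline on, 6.3 withholds the rest. Emergency unblinding does not help, because under 5.4.1 and 6.3 unblinding by the investigator itself forces discontinuation. The answer is no.

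**2. Is anyone else required to apply it?** The unblinded medical monitor *may* look at unblinded abnormal values. No frequency, trigger or route to the site is given. Section 7.4 describes regular sponsor safety review but does not say that those teams see the hidden counts. The statistician, programmer and senior managers receive unblinded summaries (6.3, 9.3.2) but have no stated role in applying stops to individual subjects. The answer is again no.

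**3. Does the gap reach the 5.4.1 stop?** That stop is an adverse event. Under Appendix 11 a laboratory abnormality becomes one when "felt to be clinically significant in the medical and scientific judgement of the investigator", so a value that the investigator never sees cannot become an event by that route. Whether any hidden value is on the list depends on the SRM. What could be missed can still be bounded.

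- Inputs: the five cell types in Protocol Table 6, assumed to make up the whole differential. W is total WBC and E is eosinophils.
- Visible sum: S = neutrophils + lymphocytes + monocytes + basophils = W − E.
- Since E ≥ 0, S ≤ W. If W is below any threshold T, then S is below T as well.
- Size of E from Protocol 4.5: 0.10 to 0.15 GI/L predicted on mepolizumab; 0.605 GI/L, the placebo median at Day 14 of the previous atopic dermatitis study; 0.5 to 0.8 GI/L assumed at baseline.
- At the SAP low-WBC flag of 1.1 GI/L (SAP 12.7.1), a true WBC of 1.1 shows as S = 1.1 − 0.15 = 0.95 to 1.1 − 0.10 = 1.00 on mepolizumab, and 1.1 − 0.605 = 0.495 at the placebo median.
- A simulation at 1.1 GI/L and at 2, 3 and 4 GI/L (the last three illustrative) gave 279,566 low-WBC cases, with 0 missed by S, as the identity requires.

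On the low side the only error is over-calling. On the high side, W can exceed T while S does not, so eosinophilia and an eosinophil-driven high WBC stay hidden.

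**4. How many hidden results could bear on a later dose?** Hematology is drawn at six scheduled visits, before dosing on dosing days (Protocol Table 3).

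| Sample | After treatment has begun? | Next scheduled dose |
|---|---|---|
| Baseline | No | Same visit |
| Week 4 | Yes | Week 8 |
| Week 8 | Yes | Week 12 |
| Week 12 | Yes | None after that visit |
| Weeks 16 and 20 | Yes | None |

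With the planned 56 randomized subjects, 56 × 2 = 112 scheduled results at most. This assumes full attendance, and that a central-laboratory result does not return before the dose given at the same visit. Hematology at unscheduled flare visits is not counted.

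**The case against.** The strongest reply is that little depends on the hidden values. Eosinophilia is only one example, and fever and rash are visible. The ALT, bilirubin, INR and cannot-monitor criteria use no blinded count. A subject who continues with raised ALT returns weekly, and the sponsor's medical monitor is told within 24 hours. A sponsor request is itself a ground for discontinuation in 5.4.1. The SAP reports no safety concerns at the interim (3.1), and a programming note (12.9.7) indicates that no liver events were reported, while allowing that some participants may have gone unreported.

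All of this narrows the point but does not close it. The 24-hour notice does not say whether it goes to the blinded or the unblinded monitor, nor that hidden counts are then examined.

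A reader might infer more than the documents support:

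- *That the 5.4.1 stop rests on blinded values and cannot fire.* The terms are in the SRM, which is not available, and the other four counts are released.
- *That a low WBC could go unseen.* The identity above rules this out.
- *That withholding the later blood count blocks a stop.* That sample follows a liver stopping event, when treatment has already been discontinued.
- *That only one role sees unblinded data.* Others do. The medical monitor is the only one named for reviewing abnormal laboratory values.
- *That 56 × 6 = 336 results are at issue.* This counts samples taken before treatment and samples with no later scheduled dose.

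**Conclusion.** The inconsistency between Appendix 8 and 6.3 is real and does not depend on the SRM. For eosinophilia, the symptomatic liver stop and the matching condition for staying on treatment cannot be applied by the site, and no other role is required to apply them. For the hematologic stop in 5.4.1 the same gap is only possible: it exists if the SRM list includes eosinophils or a high WBC driven by them.

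The size is limited. The ceiling is 112 scheduled results, and the liver stop concerns only those from subjects with ALT at or above 3xULN, a number that the documents do not give. They show no subject who was affected. The point is worth correcting because a stop stated as mandatory should have someone obliged to apply each part of it.

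**What to change.** Reconcile Protocol 5.4.1, 6.3 and Appendix 8 on two matters. First, state which blinded values, if any, count toward a mandatory stop. Second, make it a defined duty of the existing unblinded medical monitor, rather than an option, to review those values against the criteria already in the protocol and SRM, and state how that role communicates with the site without disclosing the value. No clinical threshold or stopping rule needs to change, and none is proposed here.

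Optionally, after unblinding, cross-reference SAP Listing 36 (eosinophil counts) with Listing 11 (exposure) to show any subject dosed after a blinded value met an existing criterion. Appendix 8 puts no number on eosinophilia, so the sponsor would have to state how the existing wording is read. The SAP records that the study was terminated, so this cross-reference is the part most readily done now.

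The cost is a few sentences of protocol text and one cross-reference, using a role and central-laboratory data that already exist. The downside is that a notice to the site may, in rare cases, give a weak hint of the treatment assigned.
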